- 1 * Provide a summary of the background and purpose of the study in language that can be understood by a person without a medical degree.

Schizophrenia is marked by problems in attention, memory and problem solving. These deficits predict long-term functional outcome such as the ability to live independently and maintain employment, but they are not ameliorated by currently available medications. Cognitive training improves these functions to some degree, but this approach is very time- and resource-intensive. The current project aims at enhancing and accelerating the benefits that people with schizophrenia derive from cognitive training by administering nicotine during some of the training sessions. This would provide the proof of principle for a treatment intervention that can improve cognitive symptoms of schizophrenia.

ID: VIEW4E02805CF7000
Name: v2_Lay Summary

View: v2_Justification, Objective, & Research Design

Justification, Objective, & Research Design

If you uploaded a separate research protocol document in the 'Research Protocol' page, cite the applicable section and page numbers from that document in the answer boxes below.

- 1 * Describe the purpose, specific aims, or objectives of this research. State the hypothesis to be tested:

The current project aims at determining whether the intermittent presence of nicotine during cognitive training exercises in people with schizophrenia will shorten the training period necessary to induce significant and clinically relevant improvement and enhance the improvement seen after a training period of specified length. Hypothesis 1a: Nicotine administration during training will increase the size of all measured effects of the training intervention, and will accelerate the time course of performance enhancement on the MCCB and training exercise progression parameters.

Hypothesis 1b: The larger training effects in the Nicotine Group will persist beyond the end of the intervention.

Hypothesis 2a: Within-session progress on the training exercises will be larger in the presence of nicotine than in the presence of placebo.

Hypothesis 2b: These acute nicotine-induced performance elevations will persist beyond the presence of nicotine through subsequent non-drug training sessions, giving evidence of an acute facilitation of learning processes.

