- 2 * Discuss the research design including but not limited to such issues as: probability of group assignment, potential for subject to be randomized to placebo group, use of control subjects, etc.:

Volunteers with a DSM-IV diagnosis of schizophrenia or schizoaffective disorder will be recruited, screened, and allocated in a double-blind manner to either the Nicotine Group or the Placebo Group. All participants will be asked to perform 10 weeks of cognitive remediation training (Posit Science, Duncan, SC), with daily training sessions Monday through Friday. On Mondays and Thursdays, all participants receive a lozenge 20 min prior to the training. In the Nicotine Group, the lozenge will contain 2 or 4 mg of nicotine, depending on smoking status. In the Placebo Group, the lozenge will be a matched placebo.

Outcome measures (OCMs) are assessed on Wednesdays in week 0 (day before training starts), weeks 4, 7 and 10 (after the training session), and week 14 (four weeks after training ends). OCMs are assessed on a non-drug day (Wed) because we are not studying the acute effects of nicotine but nicotine-induced enhancement of longer-term training effects.

- 3 * Describe the relevant prior experience and gaps in current knowledge. Describe any relevant preliminary data:

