
remind them to take the lozenge 20 min before the training. The participant would be allowed to keep up to two lozenges at home, for the event that they meet unexpected obstacles to coming to the MPRC on a lozenge day. Their performance would be monitored and recorded via an internet portal maintained by Posit Science Inc. Participants may take breaks but are encouraged to first complete the current exercise. We allow some flexibility in the above training and testing schedule because it will be unavoidable that some participants will be unavailable on some days. In general, if one lozenge session is missed, the lozenge will be given on the following day. If an outcome measurement day is missed, outcome measurements will be performed on either Tuesday or Friday of the same week (thus avoiding lozenge days), or if not feasible, in the preceding or following week. If an entire week of training is omitted by an otherwise reliable participant, the following weeks of the schedule will be moved back by one week.

- 2 * Describe all procedures already being performed for diagnostic or treatment purposes (if not applicable to the study, enter "N/A"):

N/A

- 3 * Describe the duration of an individual participant's participation in the study:

The cognitive training intervention will take 10 weeks. A follow-up outcome assessment session will be scheduled 4 weeks following training completion, but we will allow up to 10 weeks before a participant is labeled as "lost to follow-up". We will allow up to 3 months between consent and the next study session; after this, a participant would have to be re-consented. We will allow up to 3 months between the last nicotine exposure session and the beginning of the cognitive training. Thus, the maximum duration of participation is 12 months. If more than 3 months elapsed between the screening and the beginning of the training procedure, we would repeat most of the screening procedures prior to the start. A study physician would determine which procedure need to be repeated.

- 4 * Describe the duration of the entire study:

We anticipate that data collection will be completed in two years. Data analyses and preparation for publication may continue thereafter.

- 5 * Describe any additional participant requirements:

None.

ID: VIEW4E0280585B400

Name: v2_Study Procedures

View: v2_Sample Size and Data Analysis

Sample Size and Data Analysis

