If you uploaded a separate research protocol document in the 'Research Protocol' page, cite the applicable section and page numbers from that document in the answer boxes below.

- 1 * Provide the rationale and sample size calculations for the proposed target population:

Statistical and power analyses: Hypothesis 1a (larger or faster improvement in Nicotine than Placebo Group): Assuming training effects are linear with time, we will conduct an intention to treat (ITT) analysis by fitting the mixed model regression for repeated measures OCM= time+ treatment+ treatment x time, with time as a continuous measure. The treatment x time interaction estimates the difference between treatment groups in OCM rate of change (slope). Although we will include subjects with partial data, the effect size detectable was estimated conservatively⁷⁸ by: $d = [2(z_a + z_b)2(1-r)/bnVar(t)]/2$, where d = (difference in slopes)/SD(OCM), r = within-subject correlation of OCM, $b=4$ visits per subject, n = number of completers per group, $Var(t)=0.185$ is the within-subject variance of the visit times, and $z_a=1.96$ and $z_b=0.84$ for two-sided $\alpha=0.05$ and power=0.80. With $n=20$ completers per group, $d=0.56$ (a medium effect size) will be detectable for $r=0.7$ consistent with the high ICC of the MCCB, the primary OCM. To explore differences in treatment effects between MCCB domains, we will employ the mixed model for repeated measures: T-score= domain+ treatment+ time+ interactions. In particular, the domain x treatment x time interaction assesses variation among domains in the magnitude of the treatment effects on change slopes in OCM scores. In secondary analyses to guide the design of future studies, we will fit a model in which time is treated as a categorical measure unconstrained by a linear fit to explore different learning scenarios such as a more rapid initial acquisition but similar ceiling. In this model, we will add week 14 data to examine Hypothesis 1b (persistence of improvements after training ends), comparing treatment groups on the difference between week 14 and 10. Other exploratory analyses: 1) Smoking status (smoker, never-smoker) is added as an exploratory between-subject factor. 2) A further regression will explore differences between treatment groups in two compliance measures, the cumulative percentage of missed training sessions and lozenge administrations until each OCM time point. If treatment groups differ on compliance, we would include time-dependent compliance as a mediator of treatment effects. A descriptive analysis to support Hypothesis 1a will compare the percentage of participants in each group that achieves clinically significant improvement in MCCB composite scores (6 points from baseline adjusted for practice effects, see above) at each OCM time point.

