
Hypothesis 2a (training progress within nicotine vs. placebo sessions): For those adaptive exercise parameters for which progress is stated at the end of each session, we will compare nicotine - placebo differences on within-session progress, averaged over 20 lozenge-sessions, between treatment groups using a t-test. Power is estimated from the formula⁷⁸ $d = [2(z_a + z_b)2(1-(b-1)r)/bn]$, where d = (difference in average change)/SD(change within 1 session), $b=20$ visits per subject, and other terms are defined as above. For $n=20$ completers per group, we would have power=0.80 at two-sided $\alpha=0.05$ to detect $d=0.51$ (a medium effect size) for $r=0.3$. r is estimated based on each exercise being short and of potentially low reliability. To test Hypothesis 2b (persistence of nicotine-induced improvements beyond the presence of nicotine), we will analyze within-session progress on no-lozenge sessions. If progress made in the nicotine sessions does not persist, we would expect a performance decrement in subsequent no-lozenge sessions (Tue, Fri), whose difficulty levels begin where the previous session left off. If progress made under nicotine does persist, we would expect no decrement and progress comparable to no-lozenge sessions in the placebo group.

To achieve 20 completers per group, we expect having to enroll 25 subjects per group into the training and having to screen approximately 70 subjects in total.

Please note that screening is part of the study protocol. Thus, we expect to consent 70 subjects.

- 2 * Provide the plan for data analysis. Include in the description the types of comparisons that are planned (e.g., comparison of means, comparison of proportions, regressions, analysis of variance, etc.), which is the primary comparison/analysis, and how the analyses proposed will relate to the primary purposes of the study:

Please see above. The sample size calculation is closely related to the planned analyses.

ID: VIEW4E02806052800

Name: v2_Sample Size and Data Analysis

View: v2_Sharing of Results

Sharing of Results

- 1 * Describe whether results (study results or individual subject results, such as results of investigational diagnostic tests, genetic tests, or incidental findings) will be shared with subjects or others (e.g., the subject's primary care physicians) and if so, describe how it will be shared:

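### The week 14 minus week 10 test named for Hypothesis 1b gives the same answer whether a nicotine advantage is fully kept or never existed; Hypothesis 2b has a similar gap

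*Combined protocol and SAP*

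**What the plan says.** Justification, Objective, & Research Design, item 1, states Hypothesis 1b: "The larger training effects in the Nicotine Group will persist beyond the end of the intervention". Item 2 of that section sets outcome visits at weeks 0, 4, 7, 10 and 14, the last being four weeks after training ends.

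Sample Size and Data Analysis, item 1, tests Hypothesis 1a by the treatment-by-time slope. It then describes a model with time as categorical, introduced with "In secondary analyses to guide the design of future studies". Week 14 is added to that model, and 1b is examined by "comparing treatment groups on the difference between week 14 and 10". No other contrast is named for 1b. There is no retention margin, no rule that 1b is read only after a positive 1a, and no statement of how a non-significant result will be read.

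The only planned comparison that sets week 14 against baseline is a responder percentage reported at every outcome visit. It is labelled descriptive and assigned to 1a: "A descriptive analysis to support Hypothesis 1a will compare the percentage of participants in each group that achieves clinically significant improvement".

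For Hypothesis 2b the same section gives two patterns. For loss: "If progress made in the nicotine sessions does not persist, we would expect a performance decrement in subsequent no-lozenge sessions". For persistence: "If progress made under nicotine does persist, we would expect no decrement and progress comparable to no-lozenge sessions in the placebo group". No test or margin is named, and the analysis is not made conditional on 2a.

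**The concern.** Hypothesis 1b is about a group difference that is still present at week 14. The named contrast estimates how much that difference changed after week 10. A non-significant result fits a fully retained advantage, no nicotine effect at any time, or a loss too small for 20 per group to detect. A significant result in the direction of loss counts against 1b. The only significant result that favours nicotine is a further gain after training stops, which 1b does not claim.

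For 2b, loss does have a contrary pattern (a decrement), so that analysis can speak against persistence. But the pattern taken to show persistence is also what an inert lozenge would produce.

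Lasting benefit is the stated reason for pairing nicotine with training (Justification, Objective, & Research Design, item 3). As written, the plan has no inferential result that can show benefit at week 14, and a null 1b or 2b could be reported as persistence and carried into the design of later studies.

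**Working it through.** **The algebra.** Let D10 and D14 be the nicotine minus placebo differences in change from week 0. The planned 1b contrast is D14 − D10.

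- Never an effect: D10 = D14 = 0, contrast 0.
- Fully kept: D10 = D14 > 0, contrast 0.

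This holds for any effect size, correlation or sample size.

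**Inputs from Sample Size and Data Analysis, item 1.** n = 20 completers per group, r = 0.7, b = 4 visits, Var(t) = 0.185, two-sided 5%, power 80% (1.96 + 0.84 = 2.80).

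**Reproducing the plan's figures.**

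- 1a, taking the bracket to the power ½: d = √[2 × 2.80² × 0.3 / (4 × 20 × 0.185)] = 0.564, matching 0.56.
- 2a, with the usual factor 1 + (b − 1)r and a square root: d = √[2 × 2.80² × (1 + 19 × 0.3) / (20 × 20)] = 0.512, matching 0.51.

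Four times at 0, 1/3, 2/3 and 1 have sample variance 0.185, equal to the stated Var(t). Time therefore runs from 0 to 1 over training, and 0.56 SD is the group difference at week 10.

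**Precision of the two 1b contrasts.** Assumption: the same r between every pair of visits, including week 14.

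- Week 14 minus week 10: SE = √[2 × 2(1 − 0.7)/20] = 0.245 SD. The 95% half-width is 1.96 × 0.245 = 0.48 SD, or 86% of the 0.56 SD advantage.
- Week 14 adjusted for week 0: SE = √[2(1 − 0.7²)/20] = 0.226 SD.

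**Probability of a significant result** (normal approximation, week-10 advantage 0.56 SD):

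| State at week 14 | Planned, week 14 − 10 | Week 14 − 0, baseline-adjusted |
|---|---|---|
| Never existed | 5% | 5% |
| Fully kept | 5% | 70% |
| Half lost | 21% | 24% |
| Fully lost | 63% | 5% |

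The planned test therefore misses a half loss 79% of the time and a full loss 37% of the time. With t critical values these become 80% and 39%. The week 14 − 0 test on plain change scores has 63% power for a fully kept advantage.

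**Sensitivity to r:**

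| r | 0.5 | 0.6 | 0.7 | 0.8 | 0.9 |
|---|---|---|---|---|---|
| Full loss missed by planned test | 57% | 49% | 37% | 20% | 2% |
| Half loss missed by planned test | 86% | 83% | 79% | 71% | 49% |

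The 5% in the fully-kept and never-existed rows does not change with r.

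**Hypothesis 2b.** Using the 2a inputs (r = 0.3) and assuming 20 no-lozenge sessions, SE = √[2 × (1 + 19 × 0.3)/(20 × 20)] = 0.183 SD and the half-width is 0.36 SD, against a detectable 2a effect of 0.51 SD. A group comparison of no-lozenge progress would reject 5% of the time under no effect and 5% under full persistence. It would reject 29% of the time if half of a 0.51 SD gain is lost and 80% if all of it is lost.

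**The case against.** The strongest reply is that 1b and 2b presuppose 1a and 2a. Both hypotheses are worded as persistence of an effect already shown, and after a positive 1a slope test it is natural to ask about decay. Nothing in the plan says that a null 1b will be read as persistence. This has weight: a stated condition on 1a would largely deal with the never-existed case. But the plan does not state one, and it would not be enough. After a positive 1a, a non-significant contrast with a half-width of 0.48 SD still does not show benefit at week 14.

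Second, the categorical-time model can already yield the week 14 versus week 0 group difference, and the responder percentages cover week 14. Both are true, which is why the repair is cheap. But the model contrast is not named, and the percentages are descriptive and belong to 1a.

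Third, the size depends on assumptions. The full-loss miss rate runs from 57% to 2% as r goes from 0.5 to 0.9. If neighbouring visits correlate more strongly than distant ones, the planned contrast gains precision and the proposed one loses some. Missing a half loss is also missing partial persistence, not total failure. These points limit the miss rates but leave the algebra untouched.

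Fourth, 2b is the weaker case. Its loss pattern is explicit, and full loss would be detected about 80% of the time. Behavioral Interventions, item 1, also implies that most exercises have nearer 10 than 20 no-lozenge sessions, though that only moves the half-width to √[2 × (1 + 9 × 0.3)/(10 × 20)] × 1.96 = 0.38 SD. What remains is that the predicted persistence pattern is not specific to persistence.

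**Conclusion.** The concern holds. That the 1b contrast cannot separate a fully kept advantage from no effect needs no assumption. The figures around it (half-width 0.48 SD, full loss missed 37% of the time, half loss 79%) rest on 20 completers per group, r = 0.7 with equal correlation carried to week 14, and a week-10 advantage of 0.56 SD. Hypothesis 2b has a similar but milder gap. This should be fixed, but it is confined to secondary analyses and leaves the 1a test and the sample size as they are.

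**What to change.** For 1b, keep the categorical-time model and name as the test the between-group difference in change from week 0 to week 14, baseline-adjusted (week 0 as a covariate, or a common baseline mean), at two-sided 5%. Report week 14 minus week 10 as an estimate with its 95% confidence interval, and state that non-significance will not be read as persistence. A formal retention margin is not realistic here: to exclude loss of half of 0.56 SD with 80% power at one-sided 2.5% would take about 2 × 0.6 × 2.80²/0.28² = 120 per group.

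For 2b, interpret persistence only if 2a shows a nicotine effect, and report the group difference in no-lozenge-session progress with its 95% confidence interval instead of concluding from a null result.

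Add a sensitivity analysis using actual weeks since training ended. Study Procedures, item 3, schedules follow-up at four weeks, "but we will allow up to 10 weeks before a participant is labeled as" lost to follow-up, so the nominal week-14 visit can fall well after four weeks.

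The cost is wording only, with the same visits, data and model. The downside should be stated in the plan. For a fully kept 0.56 SD advantage the new 1b test has about 70% power (63% on change scores; 53% to 98% baseline-adjusted for r from 0.5 to 0.9; 68% and 61% at r = 0.7 with t critical values). A non-significant result would be inconclusive, not evidence of loss. A significant one would show benefit at week 14, not that all of the week-10 advantage was kept.

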3 *** Describe how the potential risks to participants are reasonable in relationship to the potential benefits:**

The risks related to administration of nicotine, cognitive training and testing, questionnaire and interview administration, handling of private information, and blood draws will be minimized as outlined above. We consider these risks to be very low in comparison with the scientific and clinical merits to be gained, which may contribute to finding a treatment intervention that can alleviate some of the most debilitating symptoms of schizophrenia.

4 *** Describe the alternatives to participation in this study. If there are no alternatives, state that participation is voluntary and the alternative is not to participate. For intervention studies, describe appropriate alternative clinical procedures or courses of treatment available to subjects.**

Participation is voluntary, and the alternative is not to participate. There are currently no FDA-approved treatments for the cognitive deficits seen in schizophrenia.

ID: VIEW4E1B5251B0400

Name: v2_Potential Benefits and Alternatives

View: v2_Withdrawal of Participants

Withdrawal of Participants

If the questions below are not applicable to the research (i.e., chart review), enter "N/A".

1 *** Describe anticipated circumstances under which subjects will be withdrawn from the research without their agreement:**

Participants may be withdrawn if they display adverse effects of nicotine that would make their continued participation in the study unsafe (see "Study Procedures" for stop criteria), if they cannot or do not follow instructions (for example, will not engage in any of the cognitive exercises despite the individually adjusted difficulty levels), or if a participant is missing too many study days (see "Study Procedures" for criteria of study exclusion).

2 *** Describe procedures for orderly termination:**

Participants are informed that their study participation is terminated, and they are paid for their time up to this time point.

3 *** Describe procedures that will be followed when subjects withdraw from the research, including partial withdrawal from procedures with continued data collection:**

Withdrawal would end any procedures associated with the study. If participants withdraw or are withdrawn due to nicotine side effects, they will be asked to stay on at the MPRC for continued monitoring until symptoms have subsided and the study physician considers it safe for them to leave.

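### Hypothesis 2a is a t-test on 20-session averages and has no rule for participants who stop training early; a session-level mixed model would use their recorded sessions and avoid a conditional bias

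*Combined protocol and SAP*

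**What the plan says.** In Sample Size and Data Analysis, item 1, the Hypothesis 2a variable is one number per participant: within-session progress on those adaptive parameters that are reported at the end of each session, "averaged over 20 lozenge-sessions, between treatment groups using a t-test". Power is given "For $n=20$ completers per group", with 20 sessions per participant. The same item states: "To achieve 20 completers per group, we expect having to enroll 25 subjects per group into the training".

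The intention-to-treat wording and the statement that participants with partial data are included belong to the Hypothesis 1a mixed model. No analysis set, minimum number of sessions, weighting or imputation is stated for Hypothesis 2a, and item 2 of that section only refers back to item 1.

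Under Withdrawal of Participants, item 3, "Withdrawal would end any procedures associated with the study". Study Procedures, item 1, moves a single missed lozenge session to the following day and shifts the schedule by a week if an otherwise reliable participant omits a whole week. It also says that the per-session progress values are recorded on all training days.

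**The concern.** Five of 25 participants per group are expected not to complete. Those who withdraw during training leave some lozenge sessions but not 20, and the plan does not say how to score them. There are two natural ways to apply the t-test, and each has a weakness.

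- **Completers only.** This selects on something that happens after randomisation and drops data already collected. If slow learners tend to leave, and one arm loses more of them, the remaining groups are no longer comparable.
- **Average of the sessions available.** If progress per session is larger early in training, an early leaver scores higher than the same person would have scored after 20 sessions. If one arm loses more people, that arm looks better for that reason alone.

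Hypothesis 2a carries the trial's evidence for an acute learning mechanism. Without a written rule, the choice between the two could be made after the data are seen.

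**Working it through.** **Inputs from the plan (Sample Size and Data Analysis, item 1).** z values 1.96 and 0.84; r = 0.3; b = 20 sessions; n = 20 completers per group; 25 per group entering training, so 5/25 = 20% non-completers. The documents give no drop-out timing, no split by arm and no learning-curve figures for within-session progress. Those are assumptions below.

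**1. The plan's own figure.** In units of the single-session SD, the variance of a mean of m sessions is V(m) = (1 + (m − 1)r)/m, so V(20) = 6.7/20 = 0.335. Then d = √[2 × 2.8² × 0.335/20] = √0.2626 = 0.512, which reproduces 0.51. The formula as it reads in the available text has a minus sign and no square root and would be negative. That may be a loss in text conversion and is not raised here.

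**2. Precision with all 25 per group.** Let 20 participants give 20 sessions and 5 give m sessions.

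- Plain average of available sessions: variance of the difference = 2 × [20 × 0.335 + 5 × V(m)]/25².
- Optimally weighted, as a mixed model does approximately: variance = 2/[20/0.335 + 5/V(m)].
- Detectable d = 2.8 × √variance.

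| m (assumed) | V(m) | d, plain average | d, weighted |
|---|---|---|---|
| 2 | 0.650 | 0.500 | 0.482 |
| 5 | 0.440 | 0.473 | 0.470 |
| 10 | 0.370 | 0.463 | 0.463 |
| 15 | 0.347 | 0.460 | 0.460 |

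For completers only, d is 0.512. Power at d = 0.51 is 0.84 to 0.87 with weighting, against 0.80.

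**3. Bias of available-session averages.** With no true effect, bias = (difference in drop-out proportion) × (leavers' early average minus the 20-session average).

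- Assume exponentially declining progress with a time constant of 10 sessions and a mean of 0.5 SD. A person with 6 sessions then averages 0.5 × [(1 − e^−0.6)/6]/[(1 − e^−2)/20] = 0.87 SD.
- With drop-out of 28% against 12% (still 20% overall) and leavers' last session spread evenly over 2 to 12, the bias is about 0.06 SD. It is 0.10 SD with a time constant of 5, and 0.03 SD with a time constant of 10 and mean progress of 0.3 SD. Simulated type I error is about 5% to 9%.
- A harsher case has 32% against 8%, all leaving after session 5, mean progress 1 SD and first-session progress four times the last. It gives 0.24 × 0.593 = 0.14 SD and 9.8% type I error.
- With constant progress, type I error stays at 4.9% even at 28% against 12%. With equal drop-out there is no bias under any of these curves.

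**4. Bias of completers only.** The SD of participants' underlying learning rates is √0.3 = 0.548. If exactly the slowest fraction p left, completers would average 0.548 × φ(z_p)/(1 − p) above the full group. That is 0.256 for p = 28% and 0.125 for p = 12%, so the bias can be at most about 0.13 SD. With imperfect selection, simulation gave about 0.09 SD and 9% to 10% type I error. With equal drop-out by arm the two terms cancel.

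**5. Session-level model on the same simulated data.** Bias was about 0.01 SD, type I error about 5%, and the standard error about 0.17, against 0.18 to 0.19 for completers only.

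**6. Runs per exercise.** Behavioral Interventions, item 1, plans five of eleven exercises per session, with each exercise on at least one lozenge day a week. Two lozenge days give 2 × 5 × 10 = 100 slots over 10 weeks, or about 9 to 10 per exercise, except sound-frequency discrimination, which is planned almost daily. With n = 20 the detectable d is √[2 × 7.84 × (1 + 9 × 0.3)/(10 × 20)] = 0.54 for b = 10, and also 0.54 for b = 9.

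**The case against.** The strongest reply is that the bias figures rest on inputs the plan does not contain. Its working assumption is linear training effects. Its remark about faster early acquisition concerns exploratory modelling of outcome measures across visits, not progress within a session. Participants also pass one or more lozenge exposure sessions before training (Study Procedures, item 1; Research Related Risks), and the 25 per group are counted at entry to training, so much nicotine intolerance will already have shown itself. The make-up rules cover isolated misses. Averaging available sessions already recovers nearly all the precision, and planned power was set on completers.

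Most of this stands. The bias is conditional, and the precision gain is mainly over the completers-only test. What remains is that withdrawal for adverse effects of nicotine is still allowed during training (Withdrawal of Participants, item 1), make-up sessions do not help someone who has left, and linearity would not cure selection among completers.

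A reader might infer that all of the expected 20% lack 20 sessions. The documents do not support that: completer is not defined, and someone lost only at the week 14 follow-up would have the full set. Nor does available-session averaging set early-curve against whole-curve groups, since each arm would hold a mixture of both.

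**Conclusion.** The gap holds: Hypothesis 2a has no stated analysis set or partial-data rule, and each natural way of applying the t-test is weaker than a model on the recorded sessions. The firmer part is precision: about 0.46 to 0.48 detectable against 0.51 for completers only, given the plan's r and 5 leavers per group, with the range set by assumed drop-out timing. The bias is illustrative: 0.03 to 0.10 SD for available-session averages if progress slows and drop-out differs by arm, and about 0.09 SD for completers only if slow learners leave and drop-out differs by arm. It is zero with equal, uninformative drop-out.

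It would be tempting to conclude that the power statement is wrong or that the planned test will be biased. Neither follows. The figure of 0.51 is correct for 20 completers with 20 sessions each, and nothing in the documents shows that drop-out will be unequal. The primary MCCB analysis is already an intention-to-treat mixed model with partial data and is not touched.

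**What to change.** Before any analysis by treatment group, replace the Hypothesis 2a t-test with this rule. For each eligible exercise parameter, analyse session-level within-session progress on lozenge days in a mixed model with treatment, exposure number for that exercise (categorical or smooth) and a random participant effect. Include every lozenge-day run from every randomised participant who started training. The treatment term tests Hypothesis 2a. Index by runs of that exercise and do not require 20, because most exercises will have about 10. Define completer, and keep the completers' t-test as a sensitivity analysis.

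The cost is a change of wording and a slightly more complex model; no new data or visits are needed. The model relies on data being missing at random given the sessions observed. It cannot recover participants lost between randomisation and the start of training, who have no sessions to analyse, so their number should be reported by arm.
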